3.0 Hypothesis

In this study we propose to address the following hypotheses: 1) Reduction in dietary sodium will decrease inflammation in patients with RA. 2) Reduction in dietary sodium will decrease blood pressure in patients with RA. 3) Reduction in dietary sodium will decrease tissue Na^+ in patients with RA.

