10.0 Statistical Methods

a. Sample Size

We will plan to enroll 50 RA patients assuming that many will drop out. The sample size estimation of n=18 was based on two outcomes of major interest: the comparison of the change from baseline for 1) DAS 28 and 2) Skin Na⁺ concentrations using a paired t-test comparing post-treatment values after receiving HS or LS diet. However, in the actual data analysis, we will compare the change from baseline to post-treatment value between the two treatment phases (i.e., linear mixed effect models) which will improve power, thus the sample size analyses presented is the most conservative. Sample size was estimated using PS-Power for a paired t-test with a 2-sided test at a significance level of 5%. Assuming that less than 20% of subjects will dropout or have incomplete data is a reasonable assumption based on our previous studies. If the number of dropouts exceeds our estimate we will replace them. For patients who are withdrawn or lost to follow-up without data for week 8 for either arm, an intention-to-treat approach will be applied. For inflammation (DAS28 score) a sample size of 18 patients will provide 95% power to detect a difference between HS and LS arms of 1.0 unit – a clinically meaningful reduction. For Skin Na⁺ measurements the standard deviation (SD) is approximately 5.0 mmol/L and a difference between groups of this magnitude represents a clinically important difference. A sample size of 18 patients will provide ~98% power to detect a difference in skin Na⁺ of 5 mmol/L, respectively. For secondary outcomes measures (e.g., inflammation (e.g., CRP, IL-6, T cell populations) and vascular function (e.g., 24 h BP) we have >95% power to detect a difference between groups equivalent to 1 SD – a difference likely to clinically relevant.

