12.0 Statistical Analysis

Baseline characteristics will be summarized for patients who are randomized to the two treatments (HS vs. LS) at baseline. A crossover design eliminates confounding due to uneven distribution of baseline variables because a patient serves as his/her own control, thus a complete balance in baseline data is obtained in the absence of dropouts.

The outcomes of interest are the comparison of the change in blood pressure, vascular stiffness (Aix, PWV), endothelial function (PAT), insulin resistance (HOMA), skin Na^+ concentrations, and inflammation (DAS28 score) between baseline and 1) after 8 weeks of HS diet, 2) after 8 weeks of LS diet. We will use Analysis of Covariance (ANCOVA) which is a form of multiple linear regression model including the blood pressure at the end of each treatment (HS and LS) or the last observation for patients with early withdrawal as an outcome variable, group variable (HS or LS) as a main independent variable, and baseline blood pressure as a covariate. By including the baseline value as a covariate, the regression coefficient for the group (HS or LS) becomes the between-group (HS vs LS) difference in the change in blood pressure response. This method is often superior to the method that used the change in blood pressure directly as the outcome variable (such as student's t-test for the change) because it adjusts for baseline differences as a covariate which reduces measurement errors more effectively.

A similar approach will be used for the vascular stiffness (Aix, PWV), endothelial function (PAT), insulin resistance (HOMA), and inflammation (DAS28 score) and skin Na^+ concentrations.

If unequal distribution of some of the variables is detected by the univariate analyses of baseline characteristics between groups, those variable will be included in a multiple linear-regression model in addition to a set of a prior chosen covariates based on clinical relevance such as age, sex, and race, with knowledge of not overfitting the model

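### The plan sizes the trial on two major outcomes, each at a full two-sided 5%, but does not say which result carries the conclusion, how the two are judged together, or consistently where blood pressure ranks

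*Combined protocol and SAP*

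**What the plan says.** Three sections of the combined protocol and SAP bear on which outcome counts.

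- **Section 10.0, Sample Size.** The figure of 18 patients is "based on two outcomes of major interest", DAS28 and skin Na+. The calculation is a paired t-test with "a 2-sided test at a significance level of 5" per cent. For DAS28, "a sample size of 18 patients will provide 95% power to detect a difference between HS and LS arms of 1.0 unit". For skin Na+, "the standard deviation (SD) is approximately 5.0 mmol/L", and about 98% power is stated for a 5 mmol/L difference. CRP, IL-6, T cell populations and "vascular function (e.g., 24 h BP") are given as examples of secondary outcomes.
- **Section 3.0, Hypothesis.** There are three numbered hypotheses, on inflammation, blood pressure and tissue Na+. The second reads "2) Reduction in dietary sodium will decrease blood pressure in patients with RA". None is marked as subordinate.
- **Section 12.0, Statistical Analysis.** The list opens "The outcomes of interest are the comparison of the change in blood pressure, vascular stiffness (Aix, PWV), endothelial function (PAT") and continues with HOMA, skin Na+ and DAS28, which makes seven measures. The ANCOVA is described for blood pressure and then extended to the others.

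No section uses the word primary for an outcome. None gives a testing order, a split of alpha, a rule that both major outcomes must succeed, or an adjustment for multiple testing. Section 12.0 states no significance level.

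**The concern.** Section 10.0 separates major from secondary outcomes, but Sections 3.0 and 12.0 do not keep the separation. A trial in which only blood pressure moved could be reported as confirming a stated hypothesis under Section 3.0, or as a secondary finding under Section 10.0, and the plan could not settle which.

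The same gap exists within the major pair. If DAS28 is significant and skin Na+ is not, or the reverse, the plan does not say whether the trial has succeeded. If either is enough and each is tested at 5%, the error rate for the pair exceeds 5%. If both are required, it does not. The outcome that carries the conclusion could then be settled after the results are known.

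**Working it through.** **Inputs from Section 10.0.** n = 18; paired t-test; two-sided alpha 0.05; skin Na+ difference 5 mmol/L with SD 5.0 mmol/L; DAS28 difference 1.0 unit with 95% power and no SD stated.

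**1. Reproducing the stated power.** Power comes from the noncentral t distribution with 17 degrees of freedom and noncentrality (difference / SD of differences) × √n.

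- Skin Na+: (5/5) × √18 = 4.24. At alpha 0.05 power is 97.9%, which matches the stated figure of about 98%. The match requires 5.0 to act as the SD of within-patient differences.
- DAS28: 95% power requires a standardised difference of 0.902, so the implied SD of differences is 1.0/0.902 = 1.11 units. This is solved backwards from the stated power and cannot verify it.

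The skin Na+ figure therefore uses the full 5% for that outcome alone. Section 10.0 states the same level for DAS28.

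**2. Chance of at least one false positive.** With k independent tests at 5% and every null hypothesis true, this is 1 − 0.95^k.

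| Outcomes counted | Calculation | Result |
|---|---|---|
| Two major outcomes (Section 10.0) | 1 − 0.95² | 9.75% |
| Three hypotheses (Section 3.0) | 1 − 0.95³ | 14.3% |
| Seven outcomes (Section 12.0) | 1 − 0.95⁷ | 30.2% |

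The outcomes are measured in the same patients, so independence is unlikely. The documents give no correlations. Simulation with equal correlations, 100,000 draws per setting, gave:

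| Assumed correlation | Two outcomes | Seven outcomes |
|---|---|---|
| 0.3 | 9.5% | 27.1% |
| 0.5 | 8.9% | 23.2% |
| 0.8 | 7.8% | 14.9% |

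**3. Power if the two major outcomes share 5%.** The least favourable step of Holm tests at 0.05/2 = 0.025. With n = 18:

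| Outcome and SD assumption | Power at 0.05 | Power at 0.025 |
|---|---|---|
| DAS28, SD of differences 1.11 | 95.0% | 90.3% |
| Skin Na+, 5.0 is the SD of differences | 97.9% | 95.3% |
| Skin Na+, 5.0 is a between-patient SD, correlation 0.3 | 92.2% | 85.8% |
| Skin Na+, 5.0 is a between-patient SD, correlation 0 | 80.7% | 70.3% |

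For the last two rows the SD of differences is 5 × √(2(1 − ρ)): 5.92 at ρ = 0.3 and 7.07 at ρ = 0. Holm can only equal or improve on the power in the right-hand column, because the second test is done at 0.05 once the first is significant.

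**The case against.** The strongest reply is that Section 10.0 already contains a hierarchy in all but name. Two outcomes determine the sample size and 24-hour blood pressure is secondary. On that reading the family is two outcomes, not seven. This stands, and it is why 9.75% is the relevant upper figure.

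A reader might infer that the trial runs a 30% risk of a false claim, or that its 5% level is broken. The documents do not support either. The 30.2% needs independence and also needs the split in Section 10.0 to be ignored. Each single test keeps its own 5% level; what is uncontrolled is the error across several claims. The 5% itself appears only as an input to the sample-size calculation. Its use in the final tests is an inference, although no other level is given.

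Sections 3.0 and 12.0 can also be read too strongly. Numbering three hypotheses does not declare them equal, and describing the ANCOVA through blood pressure may be only a worked example. That is fair, but neither section repeats the ranking in Section 10.0, so the ambiguity remains.

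Finally, Section 11.0 calls this a pilot study, and strict error control is often relaxed in small mechanistic trials. However, only the diet-adherent subset analysis is labelled exploratory, and Section 10.0 claims 95% and about 98% power for differences it calls clinically important. If an exploratory purpose is intended for all outcomes, saying so would also resolve the point.

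**Conclusion.** The point holds in a limited form. The three sections rank the outcomes inconsistently, and nothing states how DAS28 and skin Na+ are to be judged together. If either is enough for success and each is tested at 5%, the chance of at least one false positive in the pair is up to 9.75%, and about 8 to 9.5% for assumed correlations from 0.8 to 0.3. If both had to be significant, no adjustment would be needed, but the plan does not say so. A higher figure applies only if more outcomes are allowed to carry the conclusion, with 30.2% the value for all seven under independence.

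This should be corrected. It is a defect in how conclusions will be drawn, and it does not undermine the design or the sample size.

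**What to change.** Before any outcome data are seen:

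1. In Section 10.0, name DAS28 and skin Na+ as the two primary outcomes and test them with Holm at an overall two-sided 5%.
2. In Sections 3.0 and 12.0, label blood pressure and all other outcomes secondary, reported with estimates and confidence intervals and without confirmatory claims.
3. Restate paired-t power at n = 18 and alpha 0.025 as about 90% for DAS28 and about 95% for skin Na+. State the SD of differences behind each, and confirm which kind of SD the 5.0 mmol/L is. If it is a between-patient SD, the skin Na+ figure is about 86% at correlation 0.3 or 70% at correlation 0.
4. Specify the skin Na+ test as a within-patient comparison of post-treatment values. Section 6.0 schedules MRI only at visits 2 and 4, so there is no baseline value for the covariate that Section 12.0 requires.

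The cost is a change of wording plus a specified analysis for skin Na+. Stated power falls by 97.9 − 95.3 = 2.6 points for skin Na+ and 95.0 − 90.3 = 4.7 points for DAS28 under the SD assumptions in item 3. If 5.0 is a between-patient SD, the skin Na+ fall is larger: 6.4 points at correlation 0.3 and 10.4 at correlation 0. No more patients are needed if about 90% and 95% are acceptable.

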Each subject will have two MRIs. These will be performed at the end of the low-salt and high-salt phases. We will quantify Na⁺ content in skin and muscle by ²³Na MRI using a 3.0 T Phillips Achieva scanner, equipped with a ²³Na coil. Scans will be performed in the Vanderbilt University Institute of Imaging Science. This will take about an hour. Urine pregnancy testing will be performed before the MRI in women of childbearing potential. The MRI will be scheduled on the same days as visits 2 and 4 if possible; however, it is possible that for logistic reasons this may not always be possible and the MRI and in that case the MRI and clinical visits will occur on different days.

6. Microbiome specimen collection (all visits)

Stool and oral microbiota samples will be obtained from participants at each study visit. Microbiota specimens will be used to examine the relationship between microbiota and disease characteristics as well as responses to salt and will be stored for future studies.

Stool collection: Stool from a single bowel movement will be collected by the subject before each study visit. Subjects will be provided with instructions and a materials kit for collecting stool prior to the study visit. Subjects will bring collected stool to the study visit. Stool will be collected within 24 hours before the study visit and will be kept at room temperature.

Oral microbiota collection: Subjects will be asked to not brush or floss teeth within 12 hours of the scheduled assessment. Subjects will be asked to spit into a sterile container. Approximately 5 ml of saliva will be collected and frozen at each study visit.

Table 1.A Procedures and Labs - Study Summary

Procedure/Lab	Screen, virtual* *	Screen, in person	Visit 1 Baseline #1	Visit 2 HS/LS	Visit 3 Baseline #2	Visit 4 HS/LS
History	+		+	+	+	+
Exam		+	+	+	+	+

Joint Count	Self report	+	+	+	+	+
Disease activity			+	+	+	+
Aug Index			+	+	+	+
PWV			+	+	+	+
PAT			+	+	+	+
24-hr Blood pressure			+	+	+	+
Na+ MRI				+		+
CBC		+*				
ALT, AST, creatinine		+*				
Insulin			+	+	+	+
Glucose			+	+	+	+
hsCRP			+	+	+	+
ESR			+	+	+	+
Plasma			+	+	+	+
Serum			+	+	+	+
24-hr Urine			+	+	+	+
DNA/RNA			+			
Stool			+	+	+	+
Saliva			+	+	+	+
Pregnancy testing, urine		+	+	+	+	+

*Labs only drawn at in-person screening if not available from previous 12 weeks.

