11.0 Early Withdrawals and Dropouts

Intention-to-treat analysis, which focuses on all randomized patients with at least one follow-up evaluation, will be used as this has been the standard approach used by many researchers and regulatory agencies. For either, or both HS and LS treatment phases of this crossover trial, when a patient drops out without having any follow-up data assessed, data points for the patient will be excluded from the analysis. Due to the nature of the pilot study with a relatively small population, we expect that virtually all patients enrolled in the study will return for a follow-up visit, thus the number of dropouts is likely to be far less than ~20% which we built into our samples size by consenting 22 patients with goal of having at least 18 subjects' data for both treatment phases. Dropouts will be defined as patients who are randomized but never return (i.e., there is no follow-up visits).

Possible confounding could occur when a patient is included in the analysis of phase 1 and excluded from phase II due to dropout. We will re-assess baseline balance between patients who are excluded in phase I and in phase II on demographic or clinical characteristics of patients to examine potential confounding by dropouts. For patients who are withdrawn or lost to follow-up after being randomized, the last visit after baseline screen will be used to replace missing values (last observation carried forward, LOCF method). ANCOVA with LOCF method will be used to analyze the data as a more conservative approach. Exploratory analyses will also be performed by examining the findings in the subset of subjects who are adherent to the diet (\pm 20% of target Na intake).

If the participant at any time requests to withdraw from the study, he or she may do so. We will continue to store and use samples and information obtained before withdrawal unless the participant notifies the principal investigator in writing with a date of notice. In the event of withdrawal from the study, no additional collection of information from the date of withdrawal will be performed. We will enquire from participants who withdraw whether they may be contacted for future studies.

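### The claim that analysing change from baseline makes the power figures conservative is unsupported for DAS28, impossible for skin sodium, and inconsistent with the ANCOVA in Section 12

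*Combined protocol and SAP*

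**What the plan says.** **Sizing (Section 10.0, a. Sample Size).** The plan states: "The sample size estimation of n=18 was based on two outcomes of major interest", namely DAS28 and skin sodium. The method is given as: "Sample size was estimated using PS-Power for a paired t-test with a 2-sided test at a significance level of 5" percent, applied to the values after the high-salt and low-salt diets. For DAS28, "a sample size of 18 patients will provide 95% power to detect a difference between HS and LS arms of 1.0 unit", with no SD given. For skin sodium, "the standard deviation (SD) is approximately 5.0 mmol/L", and power to detect 5 mmol/L is put at about 98%. The text does not say whether 5.0 is the SD of a single measurement or of a within-patient difference.

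**The claim.** The same paragraph says the real analysis will compare change from baseline between the two phases with linear mixed effect models, "which will improve power, thus the sample size analyses presented is the most conservative".

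**The analysis section (12.0).** The model here is ANCOVA, described as a multiple linear regression. The end-of-diet value is the outcome, diet is the main independent variable and baseline is a covariate. Of this the plan says "This method is often superior to the method that used the change in blood pressure directly as the outcome variable". No patient effect is mentioned. Skin sodium is among the outcomes assessed as change from baseline, and the same approach is extended to it.

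**The MRI schedule (Section 6.0).** Each patient has two scans: "These will be performed at the end of the low-salt and high-salt phases". Table 1.A agrees, with sodium MRI at visits 2 and 4 only. DAS28 is assessed at all four visits.

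**The concern.** In a crossover, the paired comparison of post-diet values already removes each patient's stable level. Subtracting a separate baseline in each period brings in a second noisy within-patient difference. That helps only when the baseline difference predicts the post-diet difference well enough. The plan asserts the gain without condition and uses it to present its power figures as a floor.

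Three things are at stake. A reader may take 95% for DAS28 as a minimum when the analyses described can fall below it. For skin sodium, one of the two outcomes that set the sample size, neither described analysis can be run. And Sections 10.0 and 12.0 name different models, which leaves the choice open until data are in hand.

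**Working it through.** **Inputs.** From Section 10.0: n = 18 pairs, two-sided 5% paired t-test; DAS28 difference 1.0 with 95% power; skin sodium difference 5 and SD 5.0 mmol/L with about 98% power. No correlation is given anywhere, so correlations below are assumptions shown as a range.

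**Formula.** Power comes from the noncentral t with n − 1 degrees of freedom and noncentrality d√n, where d is the difference divided by the SD of within-patient differences.

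**1. The plan's own figures.**
- Skin sodium, reading 5.0 as the SD of paired differences: d = 5/5 = 1, power 97.9%. This reproduces the stated figure.
- DAS28: the SD must be back-solved. Power of 95% at n = 18 needs d = 0.9025, so the SD of differences is 1/0.9025 = 1.108.

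**2. Raw change for DAS28.** Let P be the post-diet high-minus-low difference within a patient, B the matching difference between the two period baselines, and k their correlation. With equal variances,

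Var(P − B) = 2(1 − k) Var(P), so d becomes 0.9025/√(2(1 − k)).

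| k | d | Power, n = 18 |
|---|---|---|
| 0 | 0.638 | 72.3% |
| 0.1 | 0.673 | 76.7% |
| 0.2 | 0.713 | 81.4% |
| 0.3 | 0.763 | 86.2% |
| 0.4 | 0.824 | 90.9% |
| 0.5 | 0.9025 | 95.0% |
| 0.6 | 1.009 | 98.1% |

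Break-even is at k = 0.5. If all four visits are equally correlated, as in a simple random-intercept model, the covariances of P with B cancel and k = 0. At k = 0, 22 completers give 81.4%, and 34 are needed for 95%. If the single visit 1 baseline served both periods, it would cancel and the gain would be exactly zero.

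**3. Baseline as covariate for DAS28.** Simulated with four equally correlated visits (k = 0), n = 18 and SD of paired differences 1.108:

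| Model | Correlation 0.3 | 0.5 | 0.7 |
|---|---|---|---|
| Regression of 36 values on diet and baseline, no patient term | about 91% | about 87% | about 83% |
| Random intercept, raw period baseline | 94.0% | 90.8% | 87.0% |
| Random intercept, baseline split into patient mean and within-patient deviation | 94.5% | 93.6% | 93.7% |

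Regressing P on B within patients gives about 93.5% whatever the between-visit correlation.

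**4. Skin sodium.** With scans only at visits 2 and 4, B does not exist. No change score or baseline covariate can be formed, so the power is that of the post-diet paired comparison alone. If 5.0 is instead the SD of a single measurement, the SD of differences is 5√(2(1 − ρ)), where ρ is the within-patient correlation. Power is then 80.7%, 90.4%, 95.4% and 97.9% at ρ = 0, 0.25, 0.4 and 0.5.

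**The case against.** The strongest reply is that the two sections can be reconciled. Section 12.0 says its diet coefficient represents the difference in change, and Section 10.0 names mixed models, which carry a patient effect. Read together they suggest a mixed-model ANCOVA, for which the raw-change figure of 72% is not the right one. Section 12.0 also notes that patients act as their own controls, so reading its regression without a patient term is the least charitable reading. Fitted within patients, covariate adjustment costs about 1.5 points at k = 0, roughly breaks even near k = 0.3 and gains at k = 0.5 (about 98%).

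This narrows the likely loss for DAS28 but does not support the clause. Section 10.0 specifies change as the quantity compared, Section 12.0 prefers not to analyse change, and neither writes out the combined model. Even a random-intercept ANCOVA with the raw period baseline falls to 87% in one plausible setting.

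A second reply is that Section 10.0 plans to enrol 50. At k = 0, raw change would reach 92% with 30 completers and 97.6% with 40. But the stated powers are for 18, and Section 11.0 builds in dropout "by consenting 22 patients with goal of having at least 18". Larger enrolment softens the practical consequence. It does not make the clause true, and it supplies no baseline scan.

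It is also fair that k may exceed 0.5. A DAS28 shortfall is possible, not demonstrated.

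**Conclusion.** The concern holds. For DAS28 the claimed gain in power is unsupported: the stated 95% could become anything from 72% (k = 0) to 95% (k = 0.5) under raw change, and higher only beyond k = 0.5. Under Section 12.0 read without a patient term it is about 83% to 91% for between-visit correlations of 0.7 down to 0.3. These figures rest on the back-solved SD of 1.108, equal variances at baseline and post-diet, and assumed correlations. For skin sodium the gain is impossible under the plan's own MRI schedule, whatever the correlation. Its figure of about 98% stands only if 5.0 mmol/L is the SD of paired differences. Sections 10.0 and 12.0 do not describe the same analysis. This should be corrected, though it does not by itself show that the trial is too small.

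**What to change.** 1. Delete the clause in Section 10.0 about improved power and conservative sizing.
2. Name one analysis in both sections that keeps the pairing. For DAS28 and other outcomes with period baselines, use the within-patient post-diet difference (high minus low) with the within-patient baseline difference as covariate. At k = 0 its power is about 93.5%. A mixed model with a patient effect matches this only if baseline is split into the patient mean and the within-patient deviation. State also whether period is adjusted for and how patients with one period are handled, since Section 11.0 keeps them in the analysis. With balanced sequences, a period term alone takes DAS28 from 95.0% to 94.8% and skin sodium from 97.9% to 97.8%.
3. For skin sodium, specify the paired post-diet difference with no baseline covariate, and remove it from the change-from-baseline outcomes in Section 12.0.
4. Label the assumed SDs as SDs of within-patient differences (DAS28 about 1.11, skin sodium 5.0), give their source, and show power over a range.
5. If raw change is kept for DAS28, restate its power as a range: 72% at k = 0 to 95% at k = 0.5.

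The cost is wording in Sections 10.0 and 12.0 and one short power table. The stated DAS28 power may look slightly less favourable. No patients or visits are added.
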